### 1.2 History of the Study

ETOP/7-14 NICHE trial was activated in December 2014 and the first patient was enrolled on September 2015.

The ETOP IDMC reviewed the trial safety data during its scheduled bi-annually meetings, in April 2016 (n=5 patients enrolled; no safety issues identified) and October 2016 (n=13) when the interim analysis was presented. Follow-up was suspended based on the interim analysis and an unscheduled follow-up IDMC meeting in November 2016 on the 13 enrolled patients enrolled).

At the IDMC meeting of October 2016, the interim analysis (1st stage of Simon's two-stage design) was presented. Among the first 9 patients, 5 patients (55.6%) had not reached week 12 free of progression. Thus, the stopping threshold of the 1st stage of Simon's two-stage design was reached, since more than the maximum allowed of 3 patients had a progression by 12 weeks. Based on these results, the IDMC recommended suspending further recruitment into the trial while continuing the treatment and close follow-up for the enrolled patients.

A follow-up analysis, once all enrolled patients reached the 12-week assessment, was performed in November 2016. Among all 13 enrolled patients, 6 patients (46.2%) had not reached week-12 free of progression.

Based on the data and results of the interim analysis and considering the protocol specified early stopping rule, the IDMC recommended that:

- The ETOP 7-14 NICHE trial should be permanently closed to accrual.
- Treatment and follow-up of enrolled patients may continue based on the judgement of the treating physician.
- Patients should be informed.

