#### ***Efficacy Cohort***

The efficacy cohort will include all eligible patients enrolled in the study until trial termination.

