### **3.2 Baseline characteristics**

Baseline characteristics will be summarized and presented overall **for all enrolled patients.**

All continuous variables will be summarised using the following descriptive statistics: n (non-missing sample size), mean, 95% CI for the mean, median, maximum and minimum. The frequency and percentages (based on the non-missing sample size) of observed levels will be reported for all categorical measures.

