## **4. EFFICACY ANALYSIS**

The primary efficacy analysis will include all eligible enrolled patients.

The primary endpoint is disease control, defined as complete or partial response or disease stabilisation lasting at least 12 weeks.

Results on the primary endpoint will be presented for the whole efficacy cohort as well as for the 'interim analysis' cohort.

Objective response, progression-free survival and overall survival, the secondary efficacy endpoints of the NICHE trial, will also be evaluated for the whole efficacy cohort.

Best overall response, defined as best response across all assessment time-points, during the period from enrolment to termination of trial treatment, and objective response rate, defined as the best overall response (complete or partial response) will be summarized in table format.

PFS (defined as the time between the minimum of enrolment and start treatment date until documented progression or death) and OS (defined as the time between the minimum of enrolment and start treatment date until death or last contact date for censored patients) will be summarized through tables as well as graphically depicted via Kaplan-Meier curves and alternative graphical illustrations if possible (spider plot, swimmer plot).

As an exploratory analysis, the association of the primary endpoint (Disease control at 12 weeks) with patients' baseline characteristics, prior treatments received as well as with translational results will be also investigated.

More particularly, the distribution of patients' baseline characteristics and prior treatments will be presented separately for the group of patients that achieved disease control at 12th week versus the group of patients that did not achieve disease control and corresponding Fisher's exact tests will be provided.

In a similar manner, all translational results will be presented separately for the groups of patients that achieved or not disease control. Also, PFS and OS results will be provided for selected subgroups of patients with particular interest (type of ERBB2 mutation, Gender and Smoking status). Log-rank test comparing the survival curves between subgroups will be also presented.

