## 8. LISTING OF TABLES AND FIGURES

Table 1 gives a tabulation of the following aspects unique to each table:

- Title
- Numbering
- Population
- Endpoint(s)

- Time Points or details of how to conglomerate multiple observations
- Covariates or Subgroups used to break down summary statistics
- Which summary statistics will be calculated

For figures the equivalent information is summarized in Table 2 and includes the following:

- Title
- Numbering
- Population
- Type of figure
- Endpoint(s), and which is used for horizontal and vertical co-ordinates
- Statistic(s) used in calculating co-ordinate values used in the figure
- Covariates used within the figure used to determine colours or symbols

**Table 1.** Listing of Tables

| Table title  | Number | Population      | Endpoint  | Time Points or how to conglomerate | Covariates or Subgroups | Summary Statistics             | Formal Analysis  | Notes                    |
|--|--------|-----------------|---|------------------------------------|-------------------------|--------------------------------|--|--------------------------|
| Section I: Patient Accrual & Baseline Characteristics |        |                 |   |                                    |                         |                                |  |                          |
| Accrual by center  | 1      | Efficacy cohort | Accrual   | NA                                 | center                  | n (%)                          | NA   | Sorted by descending "n" |
| Patient and tumor baseline characteristics                       | 2      | Efficacy cohort | Gender
Smoking history
ECOG Performance status (at enrolment)
TNM staging
Age (yrs at enrollment) | Baseline                           | -                       | n (%)                          | NA   |                          |
| Information on previous and subsequent lines of treatment        | 3      | Efficacy cohort | Type of prior platinum treatment
Afatinib Treatment Line
Further treatment
Type of further treatment | Baseline, Follow-up                | -                       | n (%)                          | NA   |                          |
| History of previous diseases/conditions                          | 4      | Efficacy cohort | Types of previous diseases and conditions   | Baseline                           | -                       | n (%)                          | NA   |                          |

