| Primary endpoint by baseline characteristics                       | 13     | Efficacy cohort | DC at 12w achieved or not for each value of baseline characteristics                                     | 12-week assessment  | Different values of baseline characteristics | n (%)  | Fisher's exact test     |       |
| Primary endpoint by prior treatment                                | 14     | Efficacy cohort | DC at 12w achieved or not for each value of prior treatment  | 12-week assessment  | Different types of prior treatment           | n (%)  | Fisher's exact test     |       |
| Primary endpoint by translational results                          | 15     | Efficacy cohort | DC at 12w achieved or not for each value of biomarkers centrally tested                                  | 12-week assessment  | Different status of biomarkers tested        | n (%)  | Fisher's exact test     |       |
| Progression-free survival (PFS) for selected subgroups of patients | 16     | Efficacy cohort | PFS  | PFS: time from the date of enrolment until documented progression or death without documented progression | ERBB2, gender, smoking status                | KM estimates: no. of patients, n(%) of PFS events, 12-week PFS (%) (95% CI), median PFS (in weekw) | Kaplan – Meier analysis |       |
| Overall survival (OS) for selected subgroups of patients           | 17     | Efficacy cohort | OS   | OS: time from the date of enrolment until death from any cause  | ERBB2, gender, smoking status                | KM estimates: no. of patients, n(%) of deaths, xx-weeks OS (%) (95% CI), median OS (in weeks)      | Kaplan – Meier analysis |       |

| Table title   | Number | Population    | Endpoint | Time Points or how to conglomerate                                  | Covariates or Subgroups              | Summary Statistics                                  | Formal Analysis | Notes  |
|---|--------|---------------|----------|---|--------------------------------------|---|-----------------|--|
| Section VII: Safety Analysis                                       |        |               |          |   |                                      |   |                 |  |
| (Serious) Adverse event overview  | 18     | Safety cohort | AE / SAE | At the end of each treatment visit, Within 24h of occurrence of SAE | -                                    | n (%) of persons who have experienced >=1 AE or SAE | -               |  |

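### Fisher's exact test is the only test the SAP names for disease control against baseline characteristics; it ignores the order of ages, and no age cut-point is given

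*SAP*

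**What the plan says.** SAP section 4 introduces the analysis with "As an exploratory analysis, the association of the primary endpoint (Disease control at 12 weeks) with patients' baseline characteristics", together with prior treatments and translational results. It then sets out the baseline characteristics separately for patients with and without disease control and adds that "corresponding Fisher's exact tests will be provided". Planned Table 13 in SAP section 8 repeats this. Its endpoint is "DC at 12w achieved or not for each value of baseline characteristics", its grouping is "Different values of baseline characteristics", its summary is n (%), and Fisher's exact test is the only formal analysis.

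Table 13 does not list the characteristics. Planned Table 2 in the same section does, and one of them is "Age (yrs at enrollment", with no categories. SAP 3.2 treats such variables differently for description: "All continuous variables will be summarised using the following descriptive statistics", followed by n, mean with confidence interval, median, maximum and minimum. It names no test for them.

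The population is the efficacy cohort: "The efficacy cohort will include all eligible patients enrolled in the study until trial termination". SAP 1.2 already gives the outcome: "Among all 13 enrolled patients, 6 patients (46.2%) had not reached week-12 free of progression".

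**The concern.** Fisher's exact test treats the values of a characteristic as unordered labels. That suits gender or smoking status but not age, where the question is whether older or younger patients did better.

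The SAP leaves two ways to carry out its instruction. One is a row per age, in which case the test can show almost nothing. The other is to group age, and the SAP states no cut. SAP 1.2 shows that the week-12 results were known when the plan was written, so any cut would now be chosen with the outcome in view.

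What is at stake is modest. A p-value of 1, or close to it, for age could be read as evidence of no association when the method could not have shown one. A p-value from a chosen cut could look stronger than it is.

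**Working it through.** **Inputs.** SAP 1.2 gives 6 of 13 not progression-free at week 12: 6/13 = 46.2%, which reproduces the SAP's figure. That leaves 13 − 6 = 7, so the split is taken as 7 with and 6 without disease control. This assumes that all 13 are eligible (planned Tables 9 to 11 label the efficacy cohort N=13) and that progression-free at week 12 means disease control. The SAP sets no level for exploratory tests; two-sided 5% is assumed.

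**Ungrouped, all ages distinct.** Thirteen rows of one patient each, with margins 7 and 6, allow C(13,7) = 1716 tables, each with probability 1/1716. Fisher's p sums the probabilities of all tables no more likely than the observed one: 1716 × 1/1716 = 1. This holds even if the seven controlled patients are the seven oldest. For that pattern the exact Wilcoxon p is 2/1716 = 0.0012.

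**Ungrouped, some ages tied.** With one tied pair, the smallest possible p is the chance that both members fall in the same group: [C(11,5) + C(11,7)]/1716 = (462 + 330)/1716 = 0.46. With 2, 3 and 4 tied pairs the minimum is 0.22, 0.10 and 0.049. If whole-year ages are normal with an assumed SD of 8 to 12 years, all 13 differ in only about 4% to 14% of samples, so ties are usual. Power is still only about 0.2% to 1.7% for a shift of 1.5 to 2 SD, because ties carry almost no information about order.

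**Grouped age.** Let the seven controlled patients' mean age be d SD above that of the other six, with the cut k SD above the midpoint of the two means. The chance of lying above the cut is π₁ = Φ(d/2 − k) in the seven and π₂ = Φ(−d/2 − k) in the six. If i of 7 and j of 6 lie above the cut, Fisher's p is at most 0.05 for (i, j) = (7,0), (7,1), (7,2), (6,0), (6,1), (5,0) and their mirror images (0,6), (0,5), (0,4), (1,6), (1,5), (2,6). Power is the sum over these pairs of Bin(i; 7, π₁) × Bin(j; 6, π₂).

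For d = 1.5 and k = 0, π₁ = 0.773 and π₂ = 0.227. The first six terms are 0.035, 0.062, 0.046, 0.073, 0.128 and 0.064, which sum to about 0.41; the mirror terms are negligible.

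The Wilcoxon, median-split and tertile rows below are simulated with normal ages and equal SD. The fixed-cut rows use the formula; their ranges cover a cut on either side of centre.

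| Power, two-sided 5% | 1 SD | 1.5 SD | 2 SD |
|---|---|---|---|
| Exact Wilcoxon | 30% | 60% | 84% |
| Fisher, central cut | 18.5% | 40.7% | 65.9% |
| Central cut ÷ Wilcoxon | 62% | 68% | 78% |
| Fisher, median split, favourable | 30% | 56% | 80% |
| Fisher, median split, unfavourable | 10% | 27% | 50% |
| Fisher, tertiles | 16% | 37% | 63% |
| Fisher, cut 0.5 SD off centre | 10.7–14.9% | 27.3–34.2% | 50.7–58.0% |
| Fisher, cut 1 SD off centre | 2.3–5.2% | 8.0–14.5% | 20.5–30.8% |

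The two median-split rows differ because 13 is odd. If the controlled patients tend to be older and the older half has seven patients, a 6 to 1 division rejects (p = 0.029). If the older half has six, a 5 to 1 division does not (p = 0.103), and all six must be controlled.

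**Size, and the effect of choosing the cut.** With no association, the rejection rate is 3.5% for Wilcoxon and 50/1716 = 2.9% for a median split. If the most favourable of the 12 possible cuts is taken after seeing the data, 156 of the 1716 arrangements reject: 156/1716 = 9.1%.

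**The case against.** The strongest reply is that the SAP never orders Fisher's test on raw ages. Table 13 does not name age, and its n (%) column is a layout for categories. Any sensible analyst would group age, or would just report median and range by group, which SAP 3.2 and section 4 read together arguably already provide. The analysis is exploratory, the trial closed on its stage 1 rule, and age is not among the subgroups singled out for PFS and OS. A rank test added now would also be chosen after the results. A split at the pooled median needs no look at outcome.

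Most of this stands, and it limits the point. That Table 13 covers age is an inference from Table 2 and section 4, though a natural one, since neither excludes it. The p = 1 result needs all 13 ages to be distinct, which is unlikely in whole years. A cut-point fixed in writing before the analysis would also be a fair repair. What remains is that the only test named does not fit age, and the grouping that would rescue it is not stated.

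A reader might infer that grouping costs most of the power, or that Fisher's test on grouped age detects less than half of what a rank test would. The calculations do not support that as a general statement. The figures of 10%, 27% and 50% are the unfavourable side of the median split; the favourable side gives 30%, 56% and 80%, equal or close to Wilcoxon. Most of the power is lost only with a cut well off centre, or with the unfavourable split at the smaller shifts. Nor has any defect been shown in Fisher's test for ECOG performance status, where it is valid on a few levels.

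**Conclusion.** The point holds as a minor one. Fisher's exact test is the sole test the SAP names for this comparison, age in years is a listed characteristic, and no cut-point is given. On ungrouped age the test is uninformative or nearly so. On grouped age its power depends on an unstated choice, from nearly all of the Wilcoxon power to very little; a central cut loses roughly 20% to 40% of it at shifts of 1 to 2 SD.

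The power figures rest on the assumed 7 v 6 split, normal ages with equal SD, and the two-sided 5% level. Even the better test has only 30% power at 1 SD, so a null result for age would say little either way. The primary endpoint, the stopping decision and the main conclusion are untouched.

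**What to change.** In SAP section 4 and planned Table 13, state that age will be compared between disease-control groups with the exact Wilcoxon rank-sum test, and that its median and range will be shown for each group. Keep Fisher's exact test for the categorical characteristics. If the sponsor prefers to group age, the cut-point should be written into the SAP before the table is produced, with a note that the week-12 results were already known.

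The cost is one sentence in the SAP and one extra procedure option in the analysis program. No new data are needed, and an exact test at this level keeps its size (3.5% in simulation).

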## APPENDIX

### IMPORTANT INFORMATION AS DESCRIBED IN THE PROTOCOL

#### Objectives

The **primary objective** of the study is to evaluate the ability of afatinib to control disease in pretreated patients with advanced NSCLC harbouring HER2 exon 20 mutations. More particularly, the primary endpoint is **disease control at 12 weeks**.

#### Secondary objectives

The secondary objectives of the study are:

- To evaluate secondary measures of clinical efficacy including progression-free survival (PFS),
- To assess the safety and the tolerability of the treatment.

#### Endpoints

1. Primary endpoint: Disease control at 12 weeks
2. Secondary endpoints:
  - a. Progression-free survival by RECIST v1.1
  - b. Objective response rate by RECIST v1.1
  - c. Overall survival
  - d. Adverse events graded according to CTCAE V4.0

#### Most important eligibility criteria

##### Inclusion criteria at enrolment:

- Histologically or cytologically confirmed, non-predominant squamous subtype,
- Stage IIIB (non amenable to curative-intent multimodal treatment) or IV NSCLC, according to 7th TNM classification
- Tumour is platinum-refractory
- Measurable or evaluable disease (according to RECIST 1.1 criteria)
- Locally documented HER2 mutation
- Eastern Cooperative Oncology Group (ECOG) Performance Status 0-2
- Life expectancy >3 months
- Adequate haematological, renal and hepatic function
- Effective contraception, no pregnancy

[figure not shown]
##### Exclusion criteria at enrolment:

- Mixed small-cell and non-small-cell histologic features
- Uncontrolled lepto-meningeal metastatic disease
- Previous treatment with HER2 targeted antibody or tyrosine kinase inhibitor
- Any previous (in the past 3 years) or concomitant malignancy EXCEPT adequately treated basal or squamous cell carcinoma of the skin, in situ carcinoma of the cervix or bladder, in situ ductal carcinoma of the breast
- History or presence of clinically relevant cardiovascular abnormalities

- Other serious diseases or clinical conditions, including but not limited to uncontrolled active infection and any other serious underlying medical processes that could affect the patient's capacity to participate in the trial
- Interstitial lung disease or pulmonary fibrosis
- Any concurrent systemic anticancer therapy

### Treatment

Afatinib 40 mg p.o./day until tumour progression or lack of tolerability

SCHEMA 1. Trial design

**Population:** Advanced stage NSCLC, harbouring *HER2* exon 20 mutations.

**Design:** A Phase II single-arm multicenter trial

**Planned sample size:** 22 patients

**Total trial duration:** 40 months from enrolment of the first patient, including 6 months of follow-up from enrolment of the last patient

### Statistical considerations

Simon's two stage phase II design is adopted. A Disease Control Rate (DCR) of 50% is considered as unacceptable, targeting a DCR of 75%. Hence the null hypothesis under consideration is that the  $DCR \leq 50\%$  versus the alternative that  $DCR \geq 75\%$ . For a one-sided type I error of 10% and power of 80%, a total of 22 patients are needed, with 9 patients in the first stage. If in the first stage, 6 out of the 9 patients achieve Disease Control, then the trial will proceed to the second stage and recruit an additional 13 patients for a total of 22 patients. If at least 14 out of the 22 patients achieve Disease Control, then this finding will indicate that it would be reasonable to proceed to a Phase III trial.
